The CONCERN Early Warning System:

Study Protocol and Analysis Plan

NCT03911687

INVESTIGATORS

[name], RN and [name], RN

PROTOCOL TITLE

Communicating Narrative Concerns Entered by RNs (CONCERN): Clinical Decision Support Communication for Risky Patient States

FUNDING NINR

R01NR016941

VERSION DATE

November 11, 2016:

Table of Contents

Content	Pages
I. Original Study Protocol and Statistical Analysis Plan (submitted to/funded by NINR and IRB approved)	2-4

1. Original Study Protocol and Analysis Plan

Aim 3 below is focused on the CONCERN Early Warning Score Trial Design and Analysis Plan and is excerpted from R01 grant funded in 2017 (NINR 1R01NR016941, COmmunicating Narrative Concerns Entered by RNs (CONCERN): Clinical Decision Support Communication for Risky Patient States). Protocol below was IRB approved November 2016.

Aim 3. Evaluate the impact of the CONCERN SMARTapp notification system on patient outcomes, for the primary outcomes of in-hospital mortality and length of stay (LOS) and secondary outcomes of cardiac arrest, unanticipated transfers to the intensive care unit, and 30-day hospital readmission rates.

Table 1. Sample and Setting Calendar Year 2014 (all adult patients)

Site	Beds	Occupancy Rate	In-patient Mortality	30-day Readmit	CONCERN implementation processes
PHS-BWH	777	95%	1001	18%	
PHS-NWH	300	94%	312	10%	
NYP-CUMC	745	95%	1261	18%	
NYP-Allen	300	75%	98	10%	will use open source tools, APIs (application program interfaces), web services, and SMART tools developed at Harvard Medical School. The

need for site specific, local EHR configurations will be minimized using this approach. Our technology solution will allow for continuous refinement of algorithm, pushing out a new version every 3 months to provide consistent amount of time to evaluate and track outcomes for each version.

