CONCERN Intervention Trial Design will be a multiple time-series intervention (see Table 2). Please also refer to Table 1 for study sites and samples. Baseline data will be collected at all study sites. Silent release mode (no SMARTapp notification) will be used in non-equivalent control units and as a post-intervention unit control to evaluate if notifying clinicians can decrease rates of length of stay on non-ICU units and rates of 30-day hospital readmissions. In Table 2 the different versions indicate dynamic, adaptive functionality. The adaptive function utilizes [name] inpatient acuity calculation¹¹⁸ to determine if the pattern of nursing documentation has changed. We have built in time for a "burn-in" phase to evaluate adoption and adaptation to our algorithm.

Table 2. Trial Design with Multiple Time-series Intervention

Study Arm	Site	Pre-intervention (6 months)	Phase 1 (3 months) [burn-in phase]	Phase 2a (3 months)	Phase 2b (3 months)	Phase 3 (3 months)
Control Groups	Site A	B	XX	V1 silent	V2 silent	V3 silent
	Site B	B		V1 silent	V2 silent	V3 silent
	Site A	B		V1 active	V2 active	V3 active
	Site B	B		V1 active	V2 active	V3 active

B = baseline data; none = no intervention; silent = CONCERN App will function but will not display to clinician, active = CONCERN App will display to clinician. V1=version 1; V2=version 2 refined based on continuous monitoring of data

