CONCERN intervention trial data collection and analysis includes collection of pre and post-intervention data during the 6 months before the intervention and 12 months after the intervention (see **Error! Reference source not found.** for timeline). Prior to conducting hypotheses tests, descriptive statistics will be used to describe outcome variables and key confounding variables. We propose a generalized linear mixed model to examine the impact of the CONCERN system on each of the two primary outcomes: in-hospital mortality and length of stay. This model is used to deal with combined data from multiple sites and can account for changes over time. This model allows different baselines and trajectories for different ICUs and non-ICU settings and can include both patient level and unit level covariates. We will also use a generalized linear mixed model for an interrupted time series analysis for unit level analysis. We will include a variable for closed versus open units in our analysis. We estimated statistical power for the comparison of mortality rates between the intervention and non-intervention periods and between silent and active model periods. All power calculations were based on 2-sided tests with alpha = 0.05. Using hospital patients' statistics, we expected at least 2,000 total admissions per month (ranging from 38 to 270 admissions in different units) with a mean mortality rates of 37.5 deaths per 10,000 inpatient days (ranging from 11.9 to 48.8), see Table 1. Using a very conservative number of total 50,000 inpatient days in each intervention period, we will have at least 80% statistical power to detect a difference of less than 1% relative difference in mortality rates. Because the 1% change in mortality are smaller than a clinically meaningful difference, we should have sufficient sample size. When examined by different campuses, using a very conservative value of inpatient days in one campus of 6000 inpatient days in each intervention period, we will have at least 80% statistical power to detect a difference of less than 2% relative difference in mortality rates. There is no consensus regarding the best method for analyzing length of stay. Length of stay has been analyzed using both Poisson models (or NB, or other related models such as Zero-truncated Poisson models) and survival models (such as Cox PH models).¹¹⁹ Both approaches will be applied to length of stay and the better performing model will be retained. We will use the logit link function for 30-day hospitalization outcomes. We will calculate the Number Needed to Treat during the months when the CONCERN system is on silent mode and in active mode for the non-ICU versus ICU and at each site for the

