
prevention of each of the following outcomes: length of stay, and 30-day hospital readmission rates. Additional secondary outcomes include 30-day hospital readmission, cardiac arrest, and unanticipated transfers to the ICU as well as analytics of CONCERN system log-files for clinician usage metrics. The following statistical tests will assess evaluate the reliability and validity of the results and effects of the CONCERN intervention: mutual information, association statistics including t-test and regression analysis, sub-sampling, and cross-validation and control of confounders (e.g., patient acuity with Charlson's Comorbidity Index, [name] inpatient acuity calculation¹¹⁸, and other validated acuity tools).^{3,45,57}

References from Original Protocol and Statistical Analysis Plan (NINR 1R01NR016941)

57. Goodwin L. Data mining issues and opportunities for building nursing knowledge. *J Biomed Inform*. 2003;36(4-5):379-388. doi:10.1016/j.jbi.2003.09.020.

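### The model and effect measure for length of stay, a primary outcome, are left to an undefined performance rule that trial data may settle

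*Combined protocol and SAP*

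**What the plan says.** Aim 3 of the combined protocol and SAP evaluates the system "for the primary outcomes of in-hospital mortality and length of stay (LOS"), so length of stay is co-primary with mortality.

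The paragraph on trial data collection and analysis begins with one model class: "We propose a generalized linear mixed model to examine the impact of the CONCERN system on each of the two primary outcomes". It gives no distribution or link for length of stay. It adds that the model can have starting levels and time paths that differ between ICU and non-ICU settings.

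Later the same paragraph observes that the field has not settled on a method: "Length of stay has been analyzed using both Poisson models (or NB, or other related models such as Zero-truncated Poisson models) and survival models", with Cox proportional hazards as the one survival example. The rule follows: "Both approaches will be applied to length of stay and the better performing model will be retained".

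Two other statements bear on the choice. The only order of work given is "Prior to conducting hypotheses tests, descriptive statistics will be used to describe outcome variables and key confounding variables". Among general checks on the reliability and validity of results, the plan lists "sub-sampling, and cross-validation and control of confounders", but does not tie them to this decision.

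**The concern.** A primary result should answer one question fixed before the comparison is seen. Here three things are missing: what counts as better performance, whether baseline or trial data decide, and whether the decision comes before the active/silent effect is known.

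The candidates are not two routes to one number. A count model usually gives a ratio of mean days (below 1 means shorter stays). A Cox model gives a hazard ratio for discharge (above 1 means shorter stays). Cox is also not a generalized linear mixed model as usually fitted, so the later sentence reopens what the earlier one seemed to settle. Nor is there an obvious default criterion: a Cox partial likelihood and a full count likelihood are on different footings and cannot be compared by AIC.

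At stake is mainly what the primary length-of-stay result means, and to a lesser degree its type I error.

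**Working it through.** **No plan figure to reproduce.** The power figures concern mortality only. The documents give no length-of-stay distribution, SD or effect size, so everything below rests on assumed distributions: lognormal or gamma, mean 5, 8 or 12 days, SD 0.9 to 1.2 times the mean (gamma 0.9), rounded up to whole days.

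**1. Do the two measures agree?** If every stay shortens by 2% (five assumed distributions), the mean ratio is 0.981 to 0.982 and the discharge hazard ratio 1.017 to 1.022: same direction, similar size. If only some stays change (1,000,000 simulated stays per arm):

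| Assumed stays | Pattern of change | Mean ratio | Hazard ratio |
|---|---|---|---|
| Lognormal, mean 5, SD 6 | days beyond 14 cut by 20% | 0.980 | 1.011 |
| Lognormal, mean 8, SD 7.2 | same cut; 1 day added to 20% of stays of 4 days or less | 0.980 | 1.017 |
| Gamma, mean 8, SD 7.2 | as the row above | 0.980 | 1.028 |
| Lognormal, mean 8, SD 9.6 | same cut; 1 day added to 30% of stays of 7 days or less | 0.981 | 0.999 |

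These patterns are constructed, and three of the four lengthen some short stays. They show that divergence is possible, not that it is likely.

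**2. Type I error from choosing between two valid tests.** Take the worst case, in which whichever test is significant is kept.
- Bound, independent tests: 1 − 0.95² = 0.0975. Bivariate normal: 0.0704 at correlation 0.90, 0.0646 at 0.95.
- Simulated with no effect and independent stays. An equal split of 2,000 admissions a month gives 2,000 × 3 / 2 = 3,000 per arm for one phase and 2,000 × 9 / 2 = 9,000 for three. Over 18 scenarios the robust count test rejected 4.2% to 5.9%, log-rank 4.3% to 5.6%, and either test 4.6% to 7.4%.
- A smaller simulation (500 per arm, stay = 1 + negative binomial with mean 4.5 and shape 1.2, 1,500 replicates) gave 5.1% for the negative binomial, 4.9% for Cox and 5.8% for either. The test statistics correlated at 0.98 in absolute value. A further check gave 4% to 6%.

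**3. Separate worst case: Poisson with model-based standard errors.** If variance/mean = φ, the Poisson z statistic has SD √φ under the null, so the rejection rate is 2 × [1 − Φ(1.96/√φ)].
- φ = 3.7: 1.96/1.92 = 1.02, giving 31%.
- φ = 16.7: 1.96/4.09 = 0.48, giving 63%.

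Simulation agrees (30% to 63%).

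**4. The same worst case in the plan's layout.** Table 2 gives 6 months of baseline and 9 months active or silent. For units, "we expected at least 2,000 total admissions per month (ranging from 38 to 270 admissions in different units"). Thirteen units evenly spaced from 38 to 270 average 154, and 13 × 154 = 2,002 a month, or 2,002 × 15 = 30,030 stays. The number 13 is an assumption. Null rejection rates, baseline-adjusted:
- Poisson, unit intercepts only: 29% to 64%. Negative binomial, same structure: 7% to 14%.
- Poisson with a random unit-by-period term added: 7% to 8% (REML, z test) or 4% to 6% (t, 11 df).
- Poisson, post-period comparison only, random unit intercept: 8% (300 trials).

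**5. Why the variance needs stating in any case.** The plan says "Silent release mode (no SMARTapp notification) will be used in non-equivalent control units", so units may drift differently over time. With an assumed unit-by-period drift SD of 3% to 5%, a patient-level robust variance rejected 16% to 41%. A unit-level t test (11 df) stayed at 4.0% to 6.4% over all settings tried.

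**The case against.** The best defence is that the rule is milder than it sounds. Performance ordinarily means fit or prediction, not a small p-value. A choice made on fit, blind to the intervention effect or on baseline data, costs little or no type I error. For a uniform shortening the two measures tell the same story. All of this stands, and it limits the size of the point. It does not supply the missing criterion, data source or timing. The lack of consensus on method is a reason to fix one model and report the other, not to leave the choice open.

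A reader might also infer that the rule itself brings false-positive rates of 30% to 64%. The documents do not support that:
- Those rates need Poisson to be the model retained, with model-based standard errors. Negative binomial is named alongside it, and being listed first in a sentence on past practice is not a ranking. The planned descriptive statistics would show variance well above the mean. In four simulated datasets Poisson lost to negative binomial by 5,146 to 41,954 AIC points.
- The range in the plan's layout needs a model with unit intercepts only. The plan's language on differing time paths may imply a unit-by-period term, which removes most of the excess. It does not say whether those paths vary by unit or only by setting, so it cannot be claimed that the stated mixed model fails.
- A missing variance method would matter equally with a single pre-named Poisson model. It is a separate issue from the selection rule.

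Nor do the documents say that the choice will follow the p-value. They merely do not rule it out.

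**Conclusion.** The point holds and should be corrected. As written, the plan lets trial data decide whether the primary length-of-stay result is a ratio of mean days or a discharge hazard ratio, by a rule with no criterion, data source or timing. That rests on the text alone and is certain.

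The numerical consequences are conditional on the assumed distributions. The measures usually agree but can diverge when only some stays change. Choosing between two valid tests gives about 4% to 7% against 5%. The Poisson figures belong to a worst case that the plan permits but does not prescribe, and should not be quoted as the effect of the rule.

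**What to change.** Delete the rule that retains whichever model performs better. Name one primary model and one effect measure in advance, for example a negative binomial mixed model giving the ratio of mean days, which fits the model class already stated. State a variance that allows for overdispersion and for unit-by-period variation. Report the survival model as a fixed sensitivity analysis whatever it shows.

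If a data-driven choice is kept, confine it to the six-month pre-intervention data (2,000 × 6 = 12,000 admissions at the stated monthly minimum). Use a criterion written down beforehand, compare only models for the same effect measure, and finish before any active/silent comparison.

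The cost is SAP wording. The sponsor loses the freedom to switch models, may fix on the less powerful one, and should expect somewhat wider intervals.
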